The Phase IIa portion of this study is designed as a randomized, double-blind, placebo-controlled study with only a single active study drug arm. Subjects will be randomized to receive either placebo or GLS-5310 vaccine in a 1:2 ratio. The primary and secondary goals of the Phase IIa study are the same as the Phase I study. Exploratory goals of the Phase IIa study are to determine the persistence of the immune response following vaccination with GLS-5310 and the extent of immune boosting for those who are enrolled and are seropositive at baseline. The study will be unblinded at the post-vaccination visit (study visit 4) at which time subjects will be informed of their treatment assignment. Subjects who were assigned to the placebo group will be offered to be vaccinated with GLS-5310. Subjects assigned to the placebo group who choose to be vaccinated with GLS-5310 will be followed for a year from 1st GLS-5310 vaccination (Table S4); subjects assigned to the placebo group but who decline vaccination with GLS-5310 will be followed for a year from study entry as per the original study protocol (Table S3).

Sub-studies

A sub-study will be included within the Phase IIa portion of CoV2-001 clinical trial.

Participants 66-85 years of age: 30 persons will be recruited into the study to examine whether immune responses in this age group are similar or different from those age 66-85 years of age.

The above subgroup will be randomized as part of the main study, and not separately randomized.

At randomization, the initial 5 subjects are set as the sentinel group to confirm the safety of the elderly group. When the sentinel group is vaccinated with the clinical trial drug, the vaccination is carried out at an interval of at least 24 hours between each subject. Five subjects aged 65 to 74 years will be enrolled as a sentinel group for the older age cohort. If there are no adverse drug reactions (ADRs) occurring within the 7 days after the first vaccination in the sentinel group, then enrollment into the older age cohort can proceed.

Study outcome will be based on the ITT analysis inclusive of all subgroups, however, subgroup analysis will be performed as above as an exploratory endpoint.

Sample size considerations:

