A sub-study will be included within the Phase IIa portion of CoV2-001 clinical trial.

[figure not shown]
Participants > 66-85 years of age: up to 30 persons will be recruited to examine whether immune responses in this age group are similar or different from those age < 66-85 years of age.

The above subgroup will be randomized as part of the main study, and not separately randomized.

At randomization, 5 subjects age 65 to 74 years of age will be recruited as a sentinel group to confirm the safety of the older age group. When the sentinel group is vaccinated with the clinical trial drug, the vaccination is carried out at an interval of at least 24 hours between each subject. Once five subjects aged 65 to 74 years have been enrolled into the sentinel group, if no adverse drug reactions that meet study criteria for stopping vaccination of a clinical investigational drug have not been observed, then registration of the remaining older age cohort subjects can proceed.

Exploratory goals of the Phase I study will examine (1) the effect of a single vaccination to induce IgG antibodies, and (2) whether passive transfer of immune serum from vaccinated study participants will protect against disease in an animal challenge model of SARS-CoV-2 infection. Exploratory goals of the Phase II study will examine whether (1) SARS-CoV-2 seropositive individuals at baseline experience boosting of their immune responses with vaccination and will also explore (2) the durability of vaccine induced immune responses through the assessments at long-term follow up visits, (3) immune responses differ for those who are age 66 to 85 years older relative to those age 65 and younger.

Serologic immune responses will be determined by ELISA testing with the SARS-CoV-2 spike (S) and ORF3a proteins as antigen targets. T cell responses will be determined by ELISPOT assays using overlapping 15-mer peptides spanning the entirety of the S and ORF3a proteins. Neutralizing antibody responses will be determined either by live virus, pseudovirion, or binding inhibition assay(s).

[CoV2-001 clinical trials scheme]

A summary of the vaccination evaluation is presented in Tables S2, S3 and S4.

Safety assessment: All subjects will be monitored for

- Local and systemic adverse events at each study visit.
- Laboratory-related adverse events after each vaccination.

Immune Response Assessment:

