8.1.2.1.3 Solicited local/systemic AE

In the vaccination of this investigational drug, a feeling of pulling the skin may occur due to suction, and potential adverse events of the investigational drug may include erythema, pain, heat, or partial swelling at the injection site. Other adverse events that occur are included in the unexpected adverse events.

The solicited local and systemic adverse events can be summarized as follows.

Table 8.1.2.1.3-1 Solicited local/systemic AE

Common	
 Mild to moderate administration site pain, erythema, tenderness, swelling, induration Malaise/fatigue, myalgia, or headache in the first few days following injection Visible lesion(s) at the injection site, such as erythematous papules with eschar, hypopigmentation, hyperpigmentation
Less common	
 Administration site bruising/ecchymosis, hematoma or pruritus Arthralgia or nausea Injection site hematoma, bruising/ecchymosis, laceration, other transient lesions, or bleeding related to the injection procedure Eosinophilia
Uncommon or rare	
 Administration site, laceration, other transient lesions, or bleeding related to the injection procedure Severe administration site pain or tenderness Rash following injection/EP Keloid scar or hypertrophic scar formation Transient changes in clinical laboratory values
Unknown frequency or theoretical potential risks	
 Severe localized administration site reaction, such as sterile abscess or secondary bacterial infection Allergic reaction, including urticaria, angioedema, bronchospasm, or anaphylaxis Chills, flu-like syndrome Muscle damage at the administration site Autoimmune disease Effects on the fetus and on pregnancy

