8.3.2 Stopping Rules

If any of the following situations occur, then further enrollment and Study Treatments will be halted immediately until a thorough investigation has been conducted by the Medical Monitor and PI and the IRB (if applicable):

- Any participant experiences a potentially life-threatening AE, Grade 4 AE or death assessed as related to Study Treatment;
- Any report of anaphylaxis of Grade 3 or greater assessed as related to Study Treatment.

Any SAE or death assessed as related to Study Treatment will lead to an immediate halt of study enrollment and Study Treatments, until the event has been investigated.

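### The protocol gives two different conditions for opening the 66-85 cohort after the five sentinels; one mild related reaction fails one and passes the other

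*Protocol*

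**What the plan says.** Two places in the protocol describe the sentinel step for the older cohort.

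- **Synopsis, Sub-studies.** The sentinels are defined thus: "Five subjects aged 65 to 74 years will be enrolled as a sentinel group for the older age cohort". Enrolment of the rest can go ahead on this condition: "If there are no adverse drug reactions (ADRs) occurring within the 7 days after the first vaccination in the sentinel group".
- **Section 3, Sub-studies.** Here "5 subjects age 65 to 74 years of age will be recruited as a sentinel group", and the remaining older participants can be registered "if no adverse drug reactions that meet study criteria for stopping vaccination of a clinical investigational drug have not been observed". No observation period is given.

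Other parts of the protocol fix what these conditions mean in practice.

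- **Section 8.1.2.1** defines an ADR with no severity threshold. Any unintended reaction counts if a causal link cannot be denied.
- **Section 8.1.2.1.3** puts this entry in its common category: "Mild to moderate administration site pain, erythema, tenderness, swelling, induration". It gives no percentage.
- **Section 8.3.2** halts enrolment and treatment for a short list of events. The first is: "Any participant experiences a potentially life-threatening AE, Grade 4 AE or death assessed as related to Study Treatment". The others are anaphylaxis at Grade 3 or above, and any SAE, in each case judged related.
- **Section 4.5** lists grounds for early termination. One is Grade 3 or higher events lasting a day or more in over 20% of a cohort's participants.

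The SAP does not mention the sentinels, and neither document says which condition governs.

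**The concern.** Phase I was capped at age 50 (section 4.2), so the sentinel step is the protocol's specific safety check before the 66-85 group is enrolled. A check of this kind should give one answer from one set of data. Here a reader of the synopsis and a reader of section 3 can look at the same five participants and reach different decisions. If the report does not say which condition was used, nobody can later verify that the cohort was opened according to plan.

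There is also a small mismatch in age. The protocol's exploratory objective (section 2.4) places those aged 65 in the younger group, and SAP Table 4 splits age at 66. A 65-year-old can therefore be a sentinel for a cohort to which that person does not belong.

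**Working it through.** **Setting the conditions side by side**

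| What the sentinels show | Synopsis condition | Section 3 condition (intended sense) |
|---|---|---|
| No ADR | met | met |
| One mild related site reaction, nothing worse | not met | met |
| A stopping-level ADR within 7 days | not met | not met |

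The rules part in the middle row: at least one ADR, none at stopping level. This holds whatever the ADR rate is.

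Which events fill the bottom row depends on the criteria that section 3 means. Under 8.3.2, one listed event is enough. Under the 20% ground in 4.5, one sentinel of five with a lasting Grade 3 event is exactly 20% and does not exceed the limit, while two of five is 40% and does.

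**How often the middle row occurs**

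The plan states no ADR rate and no operating characteristic for this step, so there is no figure to reproduce.

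Inputs from the protocol:
- Sentinels: n = 5.
- Allocation: "Subjects will be randomized to receive either placebo or GLS-5310 vaccine in a 1:2 ratio". For the older subgroup, "The above subgroup will be randomized as part of the main study, and not separately randomized". Each sentinel thus has a 2/3 chance of vaccine, and 5 × 2/3 ≈ 3.3 are vaccinated on average.

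Assumptions:
- p = chance of any ADR within 7 days; q = chance of a stopping-level ADR.
- Sentinels are independent, and both rules are read at 7 days.

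Formulas for the probability that the rules disagree:
- (a) all five sentinels react alike: (1 − q)^5 − (1 − p)^5
- (b) only vaccinees react: (1 − 2q/3)^5 − (1 − 2p/3)^5

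With q = 0, case (b) at p = 30% is 1 − (1 − 0.2)^5 = 1 − 0.328 = 67.2%. Case (a) at p = 30% is 1 − 0.7^5 = 1 − 0.168 = 83.2%.

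| Assumed p | (b) only vaccinees react | (a) all react alike |
|---|---|---|
| 5% | 15.6% | 22.6% |
| 10% | 29.2% | 41.0% |
| 20% | 51.1% | 67.2% |
| 30% | 67.2% | 83.2% |
| 50% | 86.8% | 96.9% |

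**Where disagreement passes one half**

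- (a): p = 1 − 0.5^(1/5) = 12.9%.
- (b): p = 1.5 × 12.9% = 19.4%.
- Allowing q = 2% raises the threshold in (a) to 1 − (0.98^5 − 0.5)^(1/5) = 16.6%.

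Placebo recipients also receive an intradermal injection, and causality is judged blind. Some of their site reactions may be recorded as ADRs, so the truth may lie between (b) and (a).

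**The case against.** The best case on the other side has five parts.

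- **The frequency of disagreement is not known.** A reader might infer that the two rules give opposite decisions in most plausible cases. The documents do not support that. They call local reactions common but give no number, and at 5% or 10% the rules agree more often than not in both variants. This stands, and the frequency can only be given as a range.
- **Closure is not written.** The synopsis says when enrolment can proceed. It does not say whether an ADR leads to closure, a pause or a review. That an ADR blocks the cohort is a natural inference, but no more. This stands too. The condition is still unmet in one place and met in the other.
- **The double negative is a slip of language.** Read literally, it reverses the condition, but only one sense is reasonable. It should be corrected, and is not evidence of a third rule.
- **The age band is stated consistently.** Both places give 65-74, so there is nothing to reconcile between them. A reader might count the absence of sentinels over 74 as an error. It is a consistently stated choice, and section 7.1 adds longer observation after vaccination for those over 75. Only the lower bound conflicts with the 66-85 definition.
- **The decision is probably past.** SAP section 4.1 describes the Phase IIa interim analysis after Visit 4 in the past tense. New wording is then unlikely to change any enrolment decision. This shifts the weight to reporting but does not remove the need for it.

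None of these reconciles the two conditions.

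**Conclusion.** The protocol contradicts itself on the condition for opening the 66-85 cohort, and the SAP does not settle it. The contradiction rests on the text alone: a single mild related site reaction fails the synopsis condition and passes that of section 3. The difference in window, and the unnamed source of the stopping criteria, add to it.

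The chance that the difference mattered depends on an ADR rate that the documents do not give. With negligible stopping-level events it is 29%, 67% and 87% at assumed vaccinee rates of 10%, 30% and 50% with no ADRs on placebo, and 41%, 83% and 97% if all sentinels react alike. Disagreement is more likely than agreement only above about 19% or 13% respectively. The mismatch at age 65 is real but minor. No view is taken on which condition is right.

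**What to change.** - Reconcile the synopsis and section 3 so that both give one condition, one observation window and one named set of stopping criteria, and remove the double negative.
- Reconcile the lower bound of the sentinel band with the definition of the 66-85 cohort.
- In the report, state which condition and window were applied to the sentinels, and list the ADRs that they had, with grade and day of onset.

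The first two items cost protocol wording. The third costs a short statement and a listing for five participants. If the cohort has already been opened, the third is the one that matters most.

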For the Phase I study, the sample size of 15 participants per group will allow detection of an increase in adverse events of 13% with 88% statistical power using a 2-sided alpha of 0.10. The sample size will allow assessment of a difference of 35% in seroconversion between groups after a complete vaccination series or after a single vaccination at a similar statistical power. The sample size will also allow assessment of a difference in geometric mean titers by ELISA, determined by analysis of variance, between dose levels (low dose versus high dose) of 35% with 86% statistical power at an alpha of 0.10. These results will be used to guide selection of vaccination regimen for Phase IIa.

For the Phase IIa study, the sample size of 300 participants, randomized 2:1 vaccine to placebo will allow detection of a difference in adverse events of 18% with 82% statistical power at alpha of 0.05. The sample size will allow assessment of a difference in seroconversion between groups of at least 10% with greater than 95% statistical power at alpha of 0.05. For a sample size of 126 participants, randomized 2:1 vaccine to placebo will yield 80% probability to detect a difference in the rate of adverse events of 28% or greater. A sample size of N=126 will allow detection of a difference in seroconversion of 14% with 80% statistical power. Safety and immunogenicity will be determined at planned Interim Analysis and after all vaccinations are completed.

Safety assessments:

Participants will be monitored at each study visit for adverse events. Laboratory safety assessments will be performed as indicated in the schedule of events to determine whether there are any changes in hematologic parameters, electrolytes, or renal function relative to pre-vaccination assessment. Subjects administered GLS-5310 will be followed for a year from their first vaccination with GLS-5310 regardless of initial study arm randomization. In the Phase IIa study, subjects, will be followed for 48 weeks from first vaccination, however, subjects assigned to placebo and who chose to be vaccinated with GLS-5310, will be followed for a year from first vaccination with GLS-5310 or a total of 60 weeks.

Immunogenicity analysis:

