- 1) Randomized to vaccine
- 2) Randomized to placebo
- 3) Subset of Placebo subjects who received vaccine after unblinding

Safety comparison will be made based on the randomization allocations and separately on the placebo randomized subject who rolled over to vaccine. These 2 vaccine groups will not be pooled.

Immunogenicity evaluation analysis method: Although this clinical trial has no statistical power to evaluate the effectiveness of a vaccine for preventing disease against SARS-CoV-2, the immune response induced by the vaccine can be evaluated by a statistical analysis. Immunogenicity results are classified as responders/non-responders and are expressed as the frequency of each assay response for each group at each time point where the evaluation is performed. The proportions of the differences between each group and an estimate of the correct 95% binomial and 95% confidence intervals are calculated. Since phase 1 clinical trials cannot secure sufficient power between administration regimens, comparisons between groups are analyzed using Fisher's Exact Test.

Similar to the safety assessments, subject who were randomized to receive Placebo who then received vaccines after the study was unblinded will be followed for immunogenicity. Results of this group will not be compared to the randomized vaccine group or pooled with the original randomized vaccine group results.

Table S2: Schedule of Events (Vaccinations at 0 and 8 weeks)

Tests and Observations	Visit 1	Visit 2	Visit 3	Tele Visit	Visit 4	Visit 5	Visit 6	Visit 7	Visit 8	Un-sched
Time relative to enrollment	Screen Enroll	Wk 1	Wk 8	Wk 9	Wk 12	Wk 16	Wk 24	Wk 36	Wk 48	N/A
Permitted window (days)		±2d	±3d	±3d	±3d	±4d	±7d	±7d	±7d	N/A
Clinical Evaluations										
Review Record Prior and Concomitant Meds	X	X	X		X	X	X	X	X	X
Physical Exam and Vital Signs ²	X	X	X		X	X	X	X	X	X
Safety Evaluations*										
Record Adverse Events	X	X	X	X	X	X	X	X	X	X
Examine injection site and record findings	X	X	X	X	X					X
Blood for Hematology ³ : CBC with differential	X	X			X				X	
Blood for Chemistry Testing ⁴ : Sodium, potassium, glucose, BUN, Cr, ALT, Bili	X	X			X				X	
Serological test ⁵	X									
Record most recent HgbA1c (diabetics only) ⁶	X									
Chest X-ray	X									
12-lead ECG	X									
PCR or Antibody test for SARS-CoV-2	X									
Urine for pregnancy testing (as applicable)	X		X							
Study Related Procedures										
Administer study drug	X		X							
Subject Diary ⁷	X	X ⁷	X		X ⁷	X	X			

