11.6 Sample Size and Randomization

This clinical trial is a phase 1/2a clinical trial to evaluate the safety and immunogenicity of GLS-5310 for the purpose of preventing COVID-19 set the required number of subjects.

For the phase 1 study, 45 subjects who meet the inclusion and exclusion criteria will be enrolled in order to secure 15 subjects to be vaccinated for investigational drugs for each vaccination group. For the phase 2a study, it was planned to secure 120 subjects based on randomization.

Randomization was performed 1:1 in groups 1b and 1c of the phase 1 study according to the pre-planned randomization generation number, and 2a, 2b in the phase 2a study to determine the difference between placebo and vaccine randomization is performed 1:2 in groups.

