7.2 General Considerations

Descriptive statistics will be used to summarize the trial results. Continuous variables will be summarized with number of subjects, means, standard deviation (SD), median, minimum, and maximum. Categorical variables will be summarized with frequency and percentage. Unless particularly specified, all tests are based on a two-sided test at a significance level of 5%.

Values that contain decimals such as mean, SD, percentages, etc. will be at the same level as the raw data for medians, minimum and maximum, plus 1 decimal place for means, and plus 2 decimals for SD. All percentages will be presented to 1 decimal place.

Details will be included in listing sorted by phases and by groups.

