11.1 Binding Antibody Responses

The binding antibody response will be classified as responder/non-responder and will be analyzed as the frequency of responses for each assay for each treatment arm at each time point at which an assessment is performed. Estimates of proportions and exact 95% Clopper-Pearson's confidence interval and exact 95% confidence interval (Chan and Zhang 1999) for the differences between the groups will be calculated. Comparison between treatment arms will be carried out using a Fisher's exact test. However, Part 1 of the study is not powered to distinguish statistical differences between dosing regimens.

The group geometric mean titer (GMT) for binding antibody endpoint titers for the SARS-CoV-2 will be calculated and the 95% confidence interval will be presented. The comparison among the administration groups of GMT will be analyzed using a two-sample t-test. Also, the geometric mean titer ratio will be calculated and its 95% confidence interval will be provided. For the GMT and the mean fold increase in GMT from baseline, the mean of the antibody that was transformed by log10 and the 95% confidence interval will be calculated and then changed back to the original unit.

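### Phase I sample size: the roughly 88% power claimed for a 35-point seroconversion difference is not delivered by 15 per arm with the planned Fisher's exact test (47–83%), and other parts of the protocol and SAP disown the claim

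*Protocol*

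**What the plan says.** The claim is in the protocol synopsis, under Sample size considerations. Its first sentence says that "the sample size of 15 participants per group will allow detection of an increase in adverse events of 13% with 88% statistical power" at a two-sided alpha of 0.10. The next says that this number is enough to examine a "difference of 35% in seroconversion between groups after a complete vaccination series or after a single vaccination at a similar statistical power". At its end, the paragraph says that the results will guide the choice of regimen for Phase IIa. Seroconversion of binding antibody is part of a primary endpoint.

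Other places bear on the claim:

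- Protocol synopsis, Immunogenicity evaluation analysis method: "Since phase 1 clinical trials cannot secure sufficient power between administration regimens, comparisons between groups are analyzed using Fisher's Exact Test".
- SAP 11.1, which also plans Fisher's exact test between arms: "Part 1 of the study is not powered to distinguish statistical differences between dosing regimens". SAP 11.2 and 11.3 repeat this.
- SAP 5 says that the trial tests no statistical hypotheses.
- SAP 7.2 says that, unless otherwise specified, "all tests are based on a two-sided test at a significance level of 5" per cent.
- Protocol 11.6, the body section on sample size, gives 15 per group and 1:1 randomization of arms 1b and 1c, but no power figure.

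**The concern.** Fifteen per arm is small for comparing two proportions, and Fisher's exact test is conservative at that size. Power near 88% for a 35-point difference therefore looks too high unless one arm responds almost never or almost always, and the protocol states no such assumption.

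The figure describes what Phase I can show on a primary endpoint, in a paragraph that links the results to the choice of regimen. At 88% power, a true 35-point difference would be missed 12% of the time. If the actual power is about one half, the comparison carries much less information than the synopsis suggests. The documents also cannot hold both positions: the synopsis claims power between groups in one paragraph and denies it in another.

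**Working it through.** **Inputs.** There are 15 per arm (synopsis; protocol 11.6), all taken as evaluable, which is the most favourable case. The difference is 35 percentage points. The test is two-sided Fisher's exact (synopsis; SAP 11.1). Alpha is 0.10, carried over from the preceding sentence, with 0.05 (SAP 7.2) as the alternative. Base rates are not stated, so the whole range from 0% versus 35% to 65% versus 100% is examined.

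**The plan's 88%.** The adverse-event figure that the seroconversion power is said to resemble matches 1 − (1 − 0.13)^15 = 1 − 0.87^15 = 87.6%. That is the chance of seeing at least one event in a single arm of 15 when the true rate is 13%. The protocol does not give its method, so this is an inference. If it is right, the 88% is not a between-group power at all.

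**Method for seroconversion.** Power(p1, p2) = Σ over i, j from 0 to 15 of Bin(i; 15, p1) × Bin(j; 15, p2) × 1[p-value(i, j) ≤ alpha], with p2 = p1 + 0.35.

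**Best case by hand, 0% versus 35%.** The first arm always shows 0/15.

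- Fisher p-value for 0/15 versus 3/15: 2 × C(15,3)/C(30,3) = 2 × 455/4,060 = 0.224.
- For 4/15: 2 × 1,365/27,405 = 0.0996, so 0.10 is met from 4 responders.
- For 5/15: 2 × 3,003/142,506 = 0.042, so 0.05 is met from 5 responders.
- Power at 0.10 = P(X ≥ 4 | 15, 0.35) = 1 − (0.0016 + 0.0126 + 0.0476 + 0.1110) = 82.7%.
- Power at 0.05 = P(X ≥ 5 | 15, 0.35) = 82.7% − 17.9% = 64.8%.

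By symmetry, 65% versus 100% gives the same results.

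**Full enumeration.**

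| True rates | Fisher, 0.10 | Fisher, 0.05 | Uncorrected chi-square, 0.10 |
|---|---|---|---|
| 0 v 35% | 82.7% | 64.8% | 93.8% |
| 2 v 37% | 75.7% | 59.1% | 88.2% |
| 5 v 40% | 67.1% | 51.9% | 82.4% |
| 10 v 45% | 57.0% | 42.9% | 75.6% |
| 20 v 55% | 48.4% | 33.9% | 65.8% |
| 32.5 v 67.5% (minimum) | 47.1% | 32.2% | 62.6% |
| 50 v 85% | 51.2% | 37.1% | 69.9% |
| 60 v 95% | 67.1% | 51.9% | 82.4% |
| 65 v 100% | 82.7% | 64.8% | 93.8% |

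On a grid of 0.1-point steps in the lower rate, Fisher at 0.10 comes within 2 points of 88% nowhere.

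**What 88% would take.** With Fisher at 0.10, a 35-point difference needs 20 per arm at 0% versus 35% and 35 per arm at 32.5% versus 67.5%. With 15 per arm, the difference detectable at 88% power is 38 points from a base rate of 0% and 52–55 points from base rates of 10–40%. For 80% power it is about 50 points at mid-range rates.

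**The case against.** The strongest reply is that the sentence names no test and no base rate and says only that the power is similar. An uncorrected chi-square at 0.10 gives 88.2% at 2% versus 37%, and an unpooled normal approximation gives 88.4% at 0% versus 35%. This stands as a limit on the point: the figure is not unobtainable by every method. But it needs a test other than the planned one and a rate at or near 0% or 100% that is stated nowhere. Pooling the two 1.2 mg arms (15 versus 30) also lets Fisher reach 88% near those extremes, but the sentence concerns 15 per group. Reading 35% as a relative difference gives absolute differences of at most 35 points, so it does not help.

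A second reply is that the claim is already disowned in the synopsis and in SAP 5 and 11.1–11.3, and is absent from protocol 11.6. That is correct and lowers the seriousness. It also identifies the sentence to correct.

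The miss rate of about one half belongs to mid-range rates. With the better arm at 95–100%, power is 67–83% and the miss rate 17–33%.

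The alpha difference is secondary. The 5% in SAP 7.2 is a default, and the 0.10 is inherited from the preceding sentence, not stated for seroconversion.

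Two stronger readings may tempt a reader:

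- **Conflict with the Phase IIa entry criterion.** If every arm must exceed 70%, passing arms differ by less than 30 points. But the criterion applies to observed rates and power to true rates. One arm may simply fail, and the claim also covers responses after a single vaccination, before the Visit 4 assessment. The wording also varies on whether each arm must pass.
- **A non-significant comparison would be taken as equivalence.** Nothing says so. Protocol 3 and 3.1 base the choice of regimen on a review of objectives, adverse events and binding antibody responses, without naming a significance test.

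**Conclusion.** The point holds. For a 35-point difference in seroconversion with 15 per arm and two-sided Fisher's exact test, power is 47–83% at alpha 0.10 and 32–65% at 0.05. The roughly 88% is reached at no pair of rates under the planned test. The range reflects the unstated base rates, and it assumes that all 15 per arm are evaluable, that 35% is an absolute difference, and that alpha 0.10 carries over from the preceding sentence. The contradiction with the synopsis's own immunogenicity paragraph and with SAP 5 and 11.1 depends on none of these assumptions.

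It should be fixed, but it does not undermine the trial. The figure appears only in the synopsis, and SAP 4.1 reports the Phase I interim analysis in the past tense, so a correction cannot alter that decision. It governs how the Phase I comparisons are described and interpreted. A reader might infer that the choice of regimen rested on this power; the documents do not show that.

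**What to change.** Either of two wording changes is enough:

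1. Replace the synopsis sentence with: *at 15 per arm, Fisher's exact test (two-sided 0.10) has 47–83% power for a 35-point difference, depending on the base rate; about 50 points are needed for 80% power at mid-range rates.*
2. Delete the power claim and state precision. For example, 11 of 15 responders is 73%, with an exact 95% confidence interval of 45–92%. This sits better with SAP 5.

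In either case, state one alpha for the Phase I comparisons in both protocol and SAP. If 5% is chosen, the power range in option 1 becomes 32–65% and the detectable difference must be recomputed.

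The cost is editing two documents and accepting a less favourable figure. No participants, visits or assays are added.

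### The 86% power quoted for a 35% Phase I GMT difference rests on an unstated SD and alpha 0.10; the SAP's t-test at 5% has about 77% under the same implied assumptions

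*Protocol*

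**What the plan says.** **Protocol synopsis, Sample size considerations.** The paragraph opens "For the Phase I study, the sample size of 15 participants per group" and makes three power claims. The last concerns GMT by ELISA, tested by analysis of variance, "between dose levels (low dose versus high dose) of 35% with 86% statistical power at an alpha of 0.10". It adds that the results will help choose the Phase IIa regimen.

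**Protocol synopsis, Immunogenicity evaluation analysis method.** The reason given for using Fisher's exact test between groups is: "Since phase 1 clinical trials cannot secure sufficient power between administration regimens".

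**SAP 7.2.** Unless a section specifies otherwise, "all tests are based on a two-sided test at a significance level of 5" per cent. No exception for Phase I GMT appears elsewhere in the SAP.

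**SAP 11.1.** For binding antibody titres: "The comparison among the administration groups of GMT will be analyzed using a two-sample t-test". A GMT ratio with a 95% CI is also planned. In the preceding responder paragraph, after Fisher's exact test, the SAP says: "Part 1 of the study is not powered to distinguish statistical differences between dosing regimens".

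**SAP section 5.** The trial is described as exploratory and descriptive, testing no statistical hypotheses. The sample size there carries no power claim, and neither does Protocol 11.6.

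**The concern.** A power figure for a comparison of mean titres means something only with an SD, an effect on a stated scale, the arms compared, the test and its alpha. The synopsis supplies the test and alpha but leaves the other three missing or ambiguous. The SAP then replaces both the test (analysis of variance becomes a t-test) and the alpha (0.10 becomes 0.05). The 86% therefore does not describe the analysis that will be reported.

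What is at stake is interpretation. Binding antibody GMT is part of a primary endpoint, and the synopsis links these results to regimen choice. Someone who trusts 86% power for a 35% difference could read a non-significant 0.6 mg v 1.2 mg comparison as good evidence that titres are similar. Nothing in either document supports that much confidence.

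**Working it through.** **Inputs**

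| Input | Value | Source |
|---|---|---|
| Arm sizes | 1a (0.6 mg) 15; 1b and 1c (1.2 mg) 15 each | Synopsis, Table S1 |
| Comparison | 15 v 15, or 15 v 30 if the 1.2 mg arms are pooled | Not stated |
| Effect | 35%: ratio 1.35, or a reduction to 0.65 | Synopsis; direction and scale not stated |
| Power and alpha | "86% statistical power at an alpha of 0.10" | Synopsis |
| Sidedness | Two-sided assumed; stated only for the adverse-event claim in the same paragraph | Synopsis |
| SD of log10 titre | None | Neither document |
| Planned test | Two-sample t-test, two-sided 5% | SAP 7.2 and 11.1 |

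**Step 1. Try to reproduce 86%.** On log10 titre let Δ be the difference, σ the SD and δ = Δ/σ. Power is the probability that a noncentral t variable with df = n1 + n2 − 2 and noncentrality λ = δ·√[n1·n2/(n1 + n2)] exceeds the two-sided critical value. Without σ this cannot be run forward, so solve for the δ that gives 86% at alpha 0.10:

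- 15 v 15: df 28, √(225/30) = 2.739, critical t 1.701. Power is 86% at δ = 1.020 (λ = 2.79).
- 15 v 30: df 43, √(450/45) = 3.162, critical t 1.681. Power is 86% at δ = 0.876 (λ = 2.77).

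**Step 2. Implied SD, σ = Δ/δ.** log10(1.35) = 0.1303 and |log10(0.65)| = 0.1871.

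| Meaning of 35% | 15 v 15 | 15 v 30 |
|---|---|---|
| Ratio 1.35 | 0.1303/1.020 = 0.128 | 0.1303/0.876 = 0.149 |
| Ratio 0.65 | 0.1871/1.020 = 0.183 | 0.1871/0.876 = 0.214 |

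With two groups, analysis of variance and the two-sided t-test are the same test. If a three-arm omnibus F-test was meant, with both 1.2 mg arms shifted equally, the implied SD for ratio 1.35 is 0.133.

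**Step 3. Same comparison and SD at the SAP's 5%.** Only the critical value changes.

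- 15 v 15: critical t 2.048, δ = 1.020, power 76.9%.
- 15 v 30: critical t 2.017, δ = 0.876, power 77.2%.
- Three-arm F-test, for reference: 77.1% at 5%.

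Because δ is fixed by the 86% claim, these results do not depend on which meaning of 35% was intended.

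**Step 4. What would give 86% at 5%?** For 15 v 15, δ must be 1.150. For ratio 1.35 the SD would have to be at most 0.1303/1.150 = 0.113 log10.

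**Step 5. Sensitivity to the SD (assumed values, illustration only; ratio 1.35, 15 v 15).**

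| SD, log10 | Power, alpha 0.10 | Power, alpha 0.05 |
|---|---|---|
| 0.128 | 86% | 77% |
| 0.15 | 75% | 63% |
| 0.2 | 54% | 41% |
| 0.3 | 32% | 21% |

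**The case against.** **The synopsis states its own alpha.** A different alpha in the SAP does not falsify 86% at 0.10. This stands. No miscalculation has been shown, because without an SD the figure can be neither confirmed nor refuted.

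**A reader might infer that 86% is wrong for the planned test whatever the SD.** It is not. An SD of 0.113 log10 or less gives at least 86% at 5% for 15 v 15 and ratio 1.35. The 77% also requires the comparison to stay the same. If 86% was worked out for 15 v 15 (SD 0.128) and the analysis pools the 1.2 mg arms, power at 5% is 88%. In the reverse case (SD 0.149, analysed 15 v 15) it is 64%. If it came from the three-arm F-test (SD 0.133), the t-test at 5% has 74% for 15 v 15 and 86% for 15 v 30. The SAP describes no pooling, and its exposure section (10.1) lists the 8-week and 12-week 1.2 mg groups separately.

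**A reader might infer that both documents concede the GMT dose comparison is underpowered.** The two sentences on insufficient power speak of regimens and sit with Fisher's test on responder proportions. They do not mention low v high dose GMT. They fit poorly beside an 86% claim for the same three arms, but they do not contradict it directly.

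**The practical risk is limited.** SAP section 5 already calls the trial descriptive. Entry to Phase IIa depends on seroconversion and related serious events, not on a GMT test. Table S1 fixes the Phase IIa arm, and the SAP reports the Phase I interim analysis in the past tense. No text says that a non-significant GMT result will be read as similarity. All of this stands, and it confines the harm to how the Phase I dose comparison is reported and interpreted.

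**Conclusion.** The point holds as a missing assumption plus a mismatch between the documents. The 86% belongs to analysis of variance at alpha 0.10 with an undisclosed SD, effect scale and set of arms. The SAP's t-test at two-sided 5% has about 77% for the same comparison and implied SD, a drop of about 9 percentage points. That result assumes a two-sided alpha in the synopsis, log10 titres with a common SD, and 86% taken as exact.

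The size of the implied SD depends on the reading: 0.128 to 0.149 log10 for a ratio of 1.35, and 0.183 to 0.214 for a 35% reduction. Whether any of these is realistic cannot be judged from the documents.

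For the same reason, a reader should not go on to conclude that the design could miss a two- to four-fold difference. That needs SDs well above those implied here, and the documents give no source for them.

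**What to change.** Do one of the following in the synopsis:

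1. Delete the 86% sentence and describe the Phase I GMT comparison as descriptive, reported as a GMT ratio with its 95% CI. SAP 11.1 already plans both.
2. Restate the power for the SAP's two-sample t-test at two-sided 5% (about 77% under the same implied assumptions). Give the SD and its source, whether 35% means a ratio of 1.35 or a reduction, and whether the comparison is 15 v 15 or 15 v 30.

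In either case, use one alpha for Phase I in both documents, and state that a non-significant dose comparison is not evidence of similar GMT.

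Do not write a detectable GMT ratio of 2.9 to 4.9 into the plan. That range (86% power, 5%, 15 v 15) comes from assuming an SD of 0.4 to 0.6 log10, which would replace one unsupported figure with another.

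The cost is a wording change in the protocol, and in the SAP if its alpha is the one changed. No participants or procedures are added. A stated figure is removed or becomes less favourable. Since the Phase I interim analysis is already done, the benefit lies in how the dose comparison is reported.
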